3.3.4 Evaluated for Safety Set (EFS)

All randomized patients will be included.

4 Trial Population

4.1 Screening Data

Available screening data include:

- Age
- Gender
- Single vs. recurrent depressive episodes

These will be reported.

4.2 Eligibility

The number of ineligible patients randomised, if any, will be reported, with reasons for ineligibility. Ineligible patients are those who do not fulfil inclusion criteria or who show exclusion criteria:

Inclusion criteria

1. Adult patients (18-75 years) with fully remitted MDD, single or recurrent, as main diagnosis confirmed by prescribing physician and SCID-5-CV (Beesdo-Baum et al., 2018; First et al., 2016)
2. Intake of SSRI/SNRI (citalopram: 20-40mg, escitalopram: 10-20mg, sertraline: 75-150mg, venlafaxine: 75-150mg, duloxetine: 60-100mg, paroxetine: 20-40mg) or NaSSA (mirtazapine: 30-45mg)
3. Discontinuation wish by patient, supported by prescribing physician
4. Fulfilment of the German S3 national guideline recommendations for treatment of Major Depressive Disorders to discontinue AM: a) response to AM, b) symptom remission for at least four months (first episode)/ 2 years (2 or more episodes with significant functional impairment) and c) concurrent intake of antidepressant medication (at least 4 weeks on a steady dose)

Exclusion criteria

1. Acute or chronic somatic illness and/or intake of medication which might interfere with depressive disorder, AM or proposed study
2. Acute suicidality, psychotic symptoms, substance abuse or addiction within the last 12 months, current mania, or hypomania confirmed by SCID-5-CV or other psychopathology which might interfere with depressive disorder, AM or proposed study
3. Any history of bipolar disorder or psychosis confirmed by SCID-5-CV
4. Severe stressful life events (e.g., death of a family member) within six months prior to study participation
5. Insufficient German language proficiency.
6. No informed consent.

7. MRI-specific exclusion criteria, if applicable: phobic anxiety, claustrophobia, ferromagnetic implants, etc.

4.3 Recruitment

A CONSORT (Schulz, Altman, & Moher, 2010) flow diagram will be used to summarise the number of patients (per treatment group where appropriate) who were:

- assessed for eligibility at screening
 1. fulfilling I/E-Criteria at screening
 2. not fulfilling I/E-Criteria at screening*
 3. post-hoc violation of I/E-Criteria*
- randomised
- not randomised*
- received the randomised treatment
- did not receive the randomised treatment*
- lost to follow-up*
- randomised and included in the primary analysis
- randomised and excluded from the primary analysis*

*reasons will be provided

4.4 Withdrawal / Follow-up

Information on the number and level of withdrawals/drop outs, number included in the analysis and the number died will be presented in CONSORT diagram format with numbers and reasons for withdrawal and/or exclusion from analysis given at each visit. Levels of withdrawal are defined as:

- Patient withdraws from treatment, but not from the study, and continues to participate in study visits
- Patient withdraws from study, but all data collected up to date withdrawal can be kept and analyzed
- Patient withdraws from study and withdraws all data

Individual missed assessment time points do not automatically lead to withdrawal from the study.

4.5 Baseline Patient Characteristics

Patients will be described with respect to major baseline demographic parameters and medical characteristic (e.g. age, gender, single vs. recurrent depressive episodes, stress ratings, prior side effects of AM, prior discontinuation experience, neuroticism, anxiety, somatosensory amplification, illness rationale of MDD, AM specifications) both, overall and separately for the four randomised groups.

Categorical data will be summarised by numbers and percentages. Continuous data will be summarised by mean, standard deviation, median, 1st and 3rd quantile, and minimum and maximum. Histograms and boxplots will be used to check the distribution and possible outliers for continuous variables. Number of available observations and number of missing observations will be presented for the treatment groups separately. Tests of statistical significance will not be undertaken for baseline characteristics; rather the clinical importance of any imbalance will be noted (Senn, 1994).

Baseline characteristics representing possible modulators

- Stress ratings:

Will be measured with the *Perceived Stress Scale* (PSS-10; Cohen et al. 1983; Klein et al. 2016), which includes ten items with five response options (0 'none of the time' to 5 'very often'). Total scores range between 0-40, with higher sum scores indicating higher perceived stress.

- **Prior side effects of AM:**

Will be measured with the *Generic Assessment of Side Effects Scale* (GASE, Rief et al. 2011). The GASE is a self-report measure including 36 symptom descriptions with 4 severity rating options (0 'not present', 1 'mild', 2 'moderate', 3 'severe'). For every reported symptom, participants indicate whether they perceive this side effect as drug-induced or not drug-induced. Medication-attributed total scores (sum of all symptom ratings, causally attributed to AM) range from 0-108, with higher scores indicating higher side effect symptom load.

- **Prior discontinuation experience:**

Will be assessed with a modified version of the Generic Rating Scale for Treatment Pre-Experiences (GEEE_{PRE}, Rief et al. 2021), i.e., two items assessing improvement (0 'no improvement' – 10 'greatest improvement imaginable') and worsening (0 'no worsening' – 10 'greatest worsening imaginable') of patient condition attributed to the most recent discontinuation attempt. A difference of improvement – worsening will be calculated, ranging from -10 to 10, with lower scores indicating a more negative discontinuation experience. Participants with no prior discontinuation experience will be assigned 0.

- **Neuroticism:**

Will be assessed with the *Emotional Stability subscale of the Brief Big Five Inventory* ([BFI-10], Rammstedt et al. 2007), i.e., two items rated on a five-step scale (1 'disagree strongly' to 5 'agree strongly'). Higher sum scores indicate higher neuroticism.

- **Anxiety (trait):**

Will be assessed with the two anxiety-related trait subscales of the *State-Trait-Anxiety-Depression-Inventory* (STADI; Laux et al. 2016, Renner et al. 2018) Each includes 5 statements with four response options (1-4). Total trait-anxiety scores base on sum scores of both anxiety subscales and range between 10 and 40, with higher sum scores indicating higher trait anxiety.

- **Somatosensory amplification:**

Will be assessed with the *Somatosensory Amplification Scale* ([SSAS], Barsky et al. 1990; Doering et al. 2015), which includes ten items rated on a five-point scale (1 'not at all true' to 5 'extremely true'). Total scores range from 10-50 with higher scores indicating more somatosensory amplification.

- **Illness rationale (single item):**

i.e., whether patients perceive their depressive disorder as a biologically or a psychologically caused illness, will be assessed with a single item ranging from 0 'biologically caused' to 10 'psychologically caused'. Lower scores indicate a more biological understanding of depressive disorders.

5 Analysis

5.1 Outcome Definitions

5.1.1 Primary endpoint

Discontinuation symptom load over the course of the experimental phase (week 2 (t2) to week 13 (t9)), will be assessed with the DESS (Rosenbaum et al., 1998), a standardized and widely used self-report measure incorporating 43 discontinuation symptoms of AM. Intensity of each discontinuation symptom will be rated on a 4-point response-scale (0 'not present', 1 'mild', 2 'moderate', 3 'severe'; Tint et al., 2008) weekly (from week 2 to week 5) or biweekly (from week 5 to week 13). Total sum scores range from 0 – 129 with higher scores indicating more pronounced discontinuation symptoms. Discontinuation symptom load will be measured as area under the curve (AUC) over all measurements from week 2 to week 13. In the model, discontinuation symptom load will be adjusted for baseline

discontinuation symptoms during run-in period reported at t1 (i.e., patients remain on their prescribed type and dose of AM but receive their pills in a new-looking, encapsulated form). AUC will be calculated using the trapezoidal rule.

5.1.2 Secondary endpoints

- a) Discontinuation symptom load over the clinical observation period (i.e. assessments from FU1 till FU3 will be considered and cover reported symptoms between week 14 until week 52) assessed by the Discontinuation Emergent Signs and Symptoms Scale (DESS; Rosenbaum et al., 1998):
As for the primary endpoint AUC will be calculated from the measurements of FU1, FU2, and FU3.
- b) Recurrence (yes / no) during experimental phase, i.e., appearance of a new depressive episode after full, sustained remission of depressive symptoms over the experimental period (i.e., assessments from t1 till t9 will be considered and cover reported symptoms between week 1 until week 13). Recurrence will be monitored weekly during run-in and (dis-)continuation phase and biweekly during monitoring phase, based on Beck Depression Inventory II and Montgomery Asberg Depression Rating Scale scores (BDI-II, Hautzinger et al., 2009; Montgomery-Asberg Depression Rating Scale [MADRS+], (Davidson et al., 1986; Schmidtke et al., 1988; Williams & Kobak, 2008). If recurrence is suspected (as indicated by BDI-II score >19 or MADRS score >21 over two study visits), corresponding SCID-5-CV sections will be conducted to (dis-)confirm recurrence (Beesdo-Baum et al., 2018; First et al., 2016).

Binary variable first recurrence of depression during experimental phase of trial (i.e. yes/no) will be given at t9.

- c) First recurrence over the course of the trial, i.e., appearance of a new depressive episode after full, sustained remission of depressive symptoms will be monitored weekly during run-in and (dis-)continuation phase, biweekly during monitoring phase, and at 26, 39, and 52 weeks post-baseline, as determined in a time-to-event analysis. Assessments from t1 till FU3 will be considered and cover reported symptoms between week 1 until week 52 based on Beck Depression Inventory II and Montgomery Asberg Depression Rating Scale scores (BDI-II, Hautzinger et al., 2009; Montgomery-Asberg Depression Rating Scale [MADRS+], (Davidson et al., 1986; Schmidtke et al., 1988; Williams & Kobak, 2008). If recurrence is suspected (as indicated by BDI-II score >19 or MADRS score >21 over two study visits), corresponding SCID-5-CV sections will be conducted to (dis-)confirm recurrence (Beesdo-Baum et al., 2018; First et al., 2016). Calendar week of start of new depressive episode will be examined and recorded.
- d) Change from baseline (t1) in patient-reported stress at t9 (12 weeks after t1), assessed with the Perceived Stress Scale (PSS-10; Cohen et al. 1983; Klein et al. 2016). The PSS-10 includes ten items with five response options (0 'none of the time' to 5 'very often'). Total scores range between 0-40, with higher sum scores indicating higher perceived stress. Difference scores will be calculated by subtracting total scores at t1 from total scores at t9, resulting in a range from -40 to 40, with higher scores indicating increased stress.
- e) Change from baseline (t1) in patient-reported state anxiety at t9 (12 weeks after t1), assessed with the two anxiety-related state subscales of the *State-Trait-Anxiety-Depression-Inventory* (STADI; Laux et al. 2016, Renner et al. 2018). Each includes 5 statements with four response options (1-4). Total state-anxiety scores base on sum scores of both anxiety subscales and range between 10 and 40, with higher sum scores indicating higher trait anxiety. Difference

scores will be calculated by subtracting total scores at t1 from total scores at t9, resulting in a range from -30 to 30, with higher scores indicating increased state-anxiety.

f) Bias scores of the emotional Posner task (Brassen et al., 2011) are the differences between reaction times to emotional faces and neutral.

In short, participants respond as fast as possible to a dot target by button pressing, while neutral, happy, sad, or fearful faces are presented as distractors. Targets are preceded by either spatially-directing cues leading to covert shifts in the attentional focus (i.e., low attentional resources to process distractors) or non-spatial cues, leaving the attentional focus on the faces. We will measure reaction times in milliseconds (ms) for each condition and calculate difference scores between the reaction times to happy and neutral faces, sad and neutral faces, as well as fearful and neutral faces under high attention to faces.

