1.3.2 Secondary endpoints

- a) Discontinuation symptom load over the clinical observation period (i.e. assessments FU1 till FU3 will be considered and cover reported symptoms between the beginning of week 14 until week 52) assessed by the Discontinuation Emergent Signs and Symptoms Scale (DESS; Rosenbaum et al., 1998)
- b) Recurrence (yes or no) over the experimental period, i.e., appearance of a new depressive episode after full, sustained remission of depressive symptoms, will be monitored weekly during run-in and (dis-)continuation phase and biweekly during monitoring phase. Assessments from t1 till t9 will be considered and cover reported symptoms between week 1 until week 13, based on Beck Depression Inventory II and Montgomery Asberg Depression Rating Scale scores (BDI-II, Hautzinger et al., 2009; Montgomery-Asberg Depression Rating Scale [MADRS+], (Davidson et al., 1986; Schmidtke et al., 1988; Williams & Kobak, 2008). If recurrence is suspected (as indicated by BDI-II score >19 or MADRS score >21 over two study visits), corresponding SCID-5-CV sections will be conducted to (dis-)confirm recurrence (Beesdo-Baum et al., 2018; First et al., 2016).
- c) First recurrence over the course of the trial, i.e., appearance of a new depressive episode after full, sustained remission of depressive symptoms will be monitored weekly during run-in and (dis-)continuation phase, biweekly during monitoring phase, and at 26, 39, and 52 weeks post-baseline, as determined in a time-to-event analysis. Assessments from t1 till FU3 will be considered and cover reported symptoms between week 1 until week 52 based on Beck Depression Inventory II and Montgomery Asberg Depression Rating Scale scores (BDI-II, Hautzinger et al., 2009; Montgomery-Asberg Depression Rating Scale [MADRS+], (Davidson et al., 1986; Schmidtke et al., 1988; Williams & Kobak, 2008). If recurrence is suspected (as indicated by BDI-II score >19 or MADRS score >21 over two study visits), corresponding SCID-5-CV sections will be conducted to (dis-)confirm recurrence (Beesdo-Baum et al., 2018; First et al., 2016). Calendar week of start of new depressive episode will be examined and recorded.
- d) Difference in patient-reported stress between baseline at t1 and 12 weeks later at t9, assessed with the Perceived Stress Scale (PSS-10; Cohen et al 1983; Klein et al 2016)

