- e) Difference in patient-reported state anxiety between baseline at t1 and 12 weeks later at t9, assessed with the two anxiety-related state subscales of the *State-Trait-Anxiety-Depression-Inventory* (STADI; Laux et al 2016; Renner et al 2018)
- f) Attentional and affective processing measured as bias scores (difference between reaction times) of happy versus neutral faces, sad versus neutral faces, and fearful versus neutral faces under high attention to faces in a modified emotional Posner task (Brassen et al., 2011)

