2.6 Timing of Outcome Assessments

See Table 1.

Table 1. Schedule of enrolment, intervention and assessments according to SPIRIT-PRO.

	STUDY PERIOD								
	Enrolment		Allocation	Experimental phase			Clinical observation		
Timepoint	S1	S2	t0	t1-t5	t6-t8	T9	FU1	FU2	FU3
Weeks	-2	-1	0	1/2/3/4/5	7/9/11	13	26	39	52
Enrolment									
Eligibility screen	✓	✓							
Informed consent			✓						
Initial consultation prescribing physician			✓						
Randomization				✓					
Interventions					✓	✓	✓		

Discontinuation versus continuation of AM High versus moderate expectation (open versus hidden treatment)			✓ ✓	✓ ✓	✓ ✓	
Assessment						
Primary outcome measures						
Discontinuation symptom load (DESS)		✓	✓	✓	✓	
Secondary outcome measures						
Discontinuation symptom load (DESS)					✓	✓
Recurrence			✓	✓	✓	✓
Psychophysiological stress (PSS-10)*		✓			✓	
State anxiety (STADI State)*		✓			✓	
Attentional, affective processing (Posner task)*					✓	
Possible modulators						
Psychophysiological stress (PSS-10)*		✓				
Side effects of antidepressant medication (GASE*)		✓			✓	
Prior discontinuation experience (GEEE _{PRE} *)		✓				
Personality traits (BFI-10)*		✓				
Trait anxiety (STADI State)*		✓				
Somatosensory amplification (SSAS)*		✓				
Illness perception (single item)		✓				
Further assessments						
Optional: rsfMRI		✓	✓ (t1)			
AM blood serum level			✓(t1)		✓	
Trait marker stress*		✓				
Adherence (single item)		✓	✓	✓	✓	✓
Self-reported depressive symptoms (BDI-II)*	✓	✓	✓	✓	✓	✓
Expert-rated depressive symptoms (MADRS)*	✓	✓	✓	✓	✓	✓
Prior discontinuation symptoms (DESS _{PAST})		✓				
Current treatment effects (GEEE _{ACT} *)		✓	✓	✓	✓	✓
Expectations (TEX-Q*)		✓	✓	✓	✓	✓
Expectations (GEEE _{EXP} *)		✓	✓	✓	✓	✓
Behavioral inhibition/approach (BIS-BAS scale)*		✓				
Psychopathology (SCID-5-CV interview)*	✓					
Well-being (SWEMWBS)		✓	✓	✓	✓	✓
Depression and Anxiety (PHQ-4)					✓	✓
Subjective Impairment (PDI*)		✓	✓(t1,t5)		✓	
Substance Use & Coping			✓(t1,t5)	✓(t7)	✓	
Screener Warmth & Competence*		✓	✓(t5)		✓	
Adverse events (single safety items)		✓	✓	✓	✓	✓
Suspicions about treatment (GEEE _{END})*					✓	
Demographic* & medical characteristics		✓			✓	✓
Debriefing & close-out						
Debriefing					✓	
Consultation prescribing physician					✓	
Individualized discontinuation plan for continuation groups						✓

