5.3.2 Analysis of Secondary Endpoints

Continuous outcomes

Linear models (ANCOVA) will be used with the following variables:

- Dependent variables:
 - AUC value based on DESS scores week 14 till week 52, i.e., assessed at FU1-FU3
 - Change from baseline (t1) of patient-reported stress scores based on PSS-10 scores at t9 (12 weeks after t1)

- Change from baseline (t1) of patient-reported state-anxiety scores based on STADI scores at t9 (12 weeks after t1)
- Independent variables:
 - Random group as two factors (i.e. 1st factor: treatment discontinuation vs continuation; 2nd factor; high vs. medium expectation) and their interaction
 - The stratification variables of the randomization process:
 - *intake duration with 24 months as a marker for long-term intake (<24 months of AM vs. >24 months)*
 - *risk of developing discontinuation symptoms associated with the antidepressant medication (moderate vs. higher or unknown risk)*
 - Concerning secondary endpoint a), the corresponding pseudo baseline value (t1) will additionally be included as covariate.

Primary interest lies in the interaction between the two factors describing the random group. The post-hoc comparisons between the subgroups will be addressed exploratively. If the corresponding p-value (for the interaction) is >0.15 the model will be calculated without the interaction and the independent main effects of the 2 factors will be assessed.

Normal distribution of the residuals will be checked graphically via a histogram of residuals. If the assumption of normally distributed residuals is clearly violated, a sensitivity analysis using the log-transformation for the dependent variable will be performed to judge the robustness of the results. Adjusted mean values and adjusted effect estimators (mean differences) with corresponding 95%-Wald confidence intervals and p-values will be given.

The ICC (intra-class correlation) will also be reported, where appropriate.

Linear mixed model (random intercept model) will be used with the following variables:

- Dependent variable:
 - Bias score (emotional versus neutral faces, measured in ms)
- Independent variables (fixed factors):
 - Expectation concerning recurrence of discontinuation symptoms derived from the factors of the random group: high expectation (open discontinuation group) versus moderate expectation (both hidden groups, continuation and discontinuation) versus low expectation (open continuation group)

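### Secondary endpoints d) and e) are defined as change from t1, but Table 1 as extracted schedules PSS-10 and STADI State only at t0 and t9; reconcile the two and adjust for the baseline score

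*SAP*

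**What the plan says.** The text uses t1 as the baseline throughout:

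- Section 1.3.2 gives d) as "Difference in patient-reported stress between baseline at t1 and 12 weeks later at t9" and e) as "Difference in patient-reported state anxiety between baseline at t1 and 12 weeks later at t9".
- Section 5.1.2 repeats this for stress ("Change from baseline (t1) in patient-reported stress at t9 (12 weeks after t1") and for anxiety ("Change from baseline (t1) in patient-reported state anxiety at t9 (12 weeks after t1"). For both it fixes the calculation: "Difference scores will be calculated by subtracting total scores at t1 from total scores at t9".
- Section 5.3.2 makes the same quantity the dependent variable, for stress as "Change from baseline (t1) of patient-reported stress scores based on PSS-10 scores at t9 (12 weeks after t1" and for state anxiety in parallel wording.

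The schedule differs. In Table 1 (Section 2.6) the secondary-outcome rows "Psychophysiological stress (PSS-10" and "State anxiety (STADI State" each show two ticks, which fall under t0 and t9. The cells for t1-t5 and t6-t8 are empty.

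For the models, Section 5.3.2 lists the two randomised factors, their interaction and the two stratification variables for all three continuous outcomes. It adds the t1 value as a covariate only for endpoint a).

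**The concern.** If Table 1 describes what was collected, the subtraction in Section 5.1.2 lacks one of its two terms. The analyst would have to depart from the written definition, most likely by substituting t0. Section 5.2 does not help: the main analysis of d) and e) uses no imputation, and multiple imputation, planned only as a sensitivity analysis, cannot recover a visit at which nobody was measured.

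The choice is more than a label. By Section 5.1.1, t1 reports on the run-in, when patients take their usual medication in a new encapsulated form. A score from t0 comes a week earlier, so the two baselines measure change from different starting points.

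A smaller matter arises in the same models. A baseline score must exist for d) and e) to be computed at all, yet it is used only by subtraction. That gives up precision at no saving.

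**Working it through.** **Interval.** Table 1 gives t0 = week 0, t1 = week 1 and t9 = week 13.

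- t9 − t1 = 13 − 1 = 12 weeks. This reproduces the stated interval, so t1 in the text is not a slip in one place.
- t9 − t0 = 13 − 0 = 13 weeks. This does not match the text.

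**Position of the ticks.** The extracted table has lost its ruling, so columns have to be fixed by rows that carry a visit label inside a cell.

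| Row in Table 1 | t0 | t1-t5 | t6-t8 | t9 |
|---|---|---|---|---|
| Substance use and coping | – | tick (t1,t5) | tick (t7) | tick |
| AM blood serum level | – | tick (t1) | – | tick |
| PDI | tick | tick (t1,t5) | – | tick |
| Optional rsfMRI | tick | tick (t1) | – | – |
| PSS-10, secondary outcome | tick | – | – | tick |
| STADI State, secondary outcome | tick | – | – | tick |

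The substance-use row fixes three consecutive columns: t1-t5, t6-t8 and t9. The PDI and rsfMRI rows show that the column to the left of t1-t5 is a separate, earlier visit. The PSS-10 and STADI State rows follow the PDI pattern with the t1-t5 cell empty. Measures taken at only some of the t1-t5 visits carry a label, and these two rows carry none.

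Two further details agree. The note to Table 1 says that only the State part of STADI is given at t9, which fits one earlier administration of the full scale. The PSS-10 row among the possible modulators is ticked at t0 alone.

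**Value of the covariate.** Let both visits have variance σ² and let r be the within-group correlation between baseline and t9. The SAP gives no value for r, so a range is assumed.

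- Residual variance of the plain change score: 2σ²(1 − r).
- Residual variance with the baseline score as covariate: σ²(1 − r²).
- Ratio: (1 − r²) / [2(1 − r)] = (1 + r)/2.

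| Assumed r | Ratio (1 + r)/2 | Reduction |
|---|---|---|
| 0.4 | 0.70 | 30% |
| 0.5 | 0.75 | 25% |
| 0.6 | 0.80 | 20% |
| 0.7 | 0.85 | 15% |

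The estimated group effect and its standard error are the same whether the dependent variable is the change or the t9 score, once the baseline score is in the model. The change definition can therefore stay.

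**The case against.** The best defence is that the table, not the text, is at fault. The t1 definition appears consistently in three sections, its 12 weeks are correct, and it matches the SAP's practice elsewhere: the primary endpoint and endpoint a) both use t1 as a pseudo baseline. A (t1) label dropped from two rows would explain everything, and both endpoints would then be computable as written. This stands as a possibility that the SAP does not exclude.

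The table is also imperfect evidence. As extracted, its upper block looks shifted: against the printed header, the randomisation tick falls under t1-t5. The follow-up DESS row appears ticked at t9 although endpoint a) uses only FU1 to FU3. The labelled rows still agree with one another on the columns from t0 to t9, so the t0 reading is likely but not certain.

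A reader might infer that d) and e) simply cannot be computed. That follows only if Table 1 is the correct side. A reader might also infer that t0 is the proper baseline because it precedes allocation. The SAP does not establish this: t0 sits under the heading Allocation, and nothing says that the questionnaires come first. If t1 scores exist, the SAP gives no ground for overriding them.

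On the covariate, an unadjusted change score is a valid analysis in a randomised comparison, and both endpoints are exploratory (Sections 2.4 and 3.1). That is right: the omission is not an error, and the gain is in precision only.

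**Conclusion.** The text and the schedule contradict each other on the baseline visit for 2 of 6 secondary endpoints, and the SAP does not show which is right. The direct consequence is an undefined baseline: t1 with a 12-week interval, or t0 with a 13-week interval. The conclusion rests on the extracted table, whose labelled rows support the t0 reading, and it needs only a comparison with the original table or the case report forms to resolve.

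Separately, adjusting d) and e) for whichever baseline score is used is a free improvement. The 30% to 15% reduction assumes equal variances at the two visits and a correlation of 0.4 to 0.7. It also takes the baseline score as unaffected by group, as the SAP already does when it adjusts the primary endpoint for t1. The reduction is relative to a plain change score and says nothing about the baseline contradiction itself.

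Both endpoints are exploratory and the primary analysis is untouched. This should be corrected before the t9 analysis but does not threaten the trial's main conclusion.

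**What to change.** Before analysis, check at which visits PSS-10 and STADI State were given, and state one baseline visit for both endpoints in Sections 1.3.2, 5.1.2 and 5.3.2 and in Table 1:

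- If they were given only at t0, redefine both endpoints as change from t0 to t9, with an interval of 13 weeks.
- If they were given at t1, keep the t1 definition and the 12 weeks, and add the (t1) tick to both rows of Table 1.

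In either case, extend the covariate line in Section 5.3.2, now limited to endpoint a), so that the chosen baseline PSS-10 or STADI State score enters the model for d) and e) respectively.

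The cost is SAP wording. No new data are needed, because computing the change already requires the baseline score, and the covariate uses one degree of freedom in each model.
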